To address the above gaps in knowledge, we designed and are close to finishing an original 2-year, randomized, controlled 1:1 RCT (continue vs discontinue), rater-blinded DMT discontinuation study (DISCOMS, NCT#: 03073603). The last of 260 patients was enrolled on February 4, 2020. Last patient, last visit will be in August 2021 (note, not all will be followed for two years, with shortest final follow-up at 18 months in a minority of late enrollees). While this is the first RCT of DMT discontinuation, others are underway in France (NCT03653273) and The Netherlands (NCT04260711). Among focus groups employed during the operation of DISCOMS, it was very clear that one of the main limitations of the study was relatively short duration of the follow-up. Herein we propose to address this limitation with a non-randomized, yet rater-blinded protocol to extend the follow-up of 100 participants from the original DISCOMS cohort by at least 12 months. In essence, the first 100 participants from the DISCOMS primary study who have already successfully completed the primary DISCOMS study (i.e. did not fail on the primary outcome of a new relapse or Brain MRI lesion), retained their original drug assignment (continue or discontinue) at the end of their participation in DISCOMS, and agree to participate in the extension will be included for a minimum of 12 more months of follow-up as assessed at a single visit. This is a pragmatic clinical trial, based on real world patterns of patient decision-making. As such, study visits will be attached to routine office visits when possible, and the patient/their insurance will be responsible for payment of standard of care aspects related to the study. This will include drug costs, the annual brain MRI scans at year one, and all routine safety monitoring as would be obtained in a typical office setting for that individual medication. The funding agency, EMD Serono (a biopharmaceutical business of Merck Pharmaceuticals KGaA), will be responsible financially for all research aspects, including data acquisition, all research personnel, and all regulatory review. In addition, while this is a discontinuation trial, all patients will be aware of their medication assignment, while observers of the main outcomes (relapses, MRI changes and the EDSS) will be blinded.

III. Research Methods

A. Outcome Measure(s):

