What is the main reason you participated in the DISCOMS extension study? Please circle one.

a) To possibly stop my MS medication, b) Increased access to doctor, nurse, and study team, c) Increased monitoring of my disease, ex. more frequent MRI, d) Possibility of saving money by going off my MS medication, e) Participation in clinical research to further medical knowledge of MS, f) Other: Please list other reason(s)

What is the main reason you stayed in the extension study? Please circle one.

a) To possibly stop my MS medication, b) Increased access to doctor, nurse, and study team, c) Increased monitoring of my disease, ex. more frequent MRI, d) Participation in clinical research to further medical knowledge of MS, e) Other: Please list other reason(s)

B. Description of Population to be Enrolled:

Inclusion criteria:

- Participation in and completion of the DISCOMS trial (NCT# 03073603) for a minimum of 18 and maximum of 24 months (i.e., it is possible some will have been enrolled late enough in the primary study so as to not have completed the full 24 months).
 - Only include participants in the following study groups:
 - Randomized to the discontinue group, stayed off their DMT throughout and after the trial
 - Randomized to the continue group, continuously* stayed on their DMT throughout and after the trial
- Must be willing to continue in their previously-assigned treatment group for the entire, additional 12-Month follow-up period. For those in the continue group, the participant may have switched to a generic or biosimilar version of their medication, or to a different approved medication, if due to intolerance, convenience or insurance mandates, but NOT if due to having new or worsening MS disease activity.
- RRMS, SPMS, or PPMS by McDonald 2010 criteria⁹. Patients will be defined by subtype based on 2013 updated phenotypic criteria¹⁶. Progression of MS will be defined by the local principal investigator either prospectively with an EDSS change of at least 1.0 points over the last two years, or retrospectively, with any significant change in motor function over at least one year, unrelated to relapse.

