- During the primary DISCOMS study, no evidence of recent new inflammatory disease activity (inactive by the Lublin criteria¹⁶). Pseudorelapses due to infection, fever, or other stressors as deemed by the local PI will NOT be excluded. Those who have already successfully completed the primary DISCOMS study without having a new relapse or MRI scan change, but who have a relapse or scan change AFTER ending participation in DISCOMS but before entering the extension ARE eligible and will be recruited, i.e. we do not wish to undercount new activity that occurs after exiting DISCOMS.
- Provides informed consent to continue in the extension trial.
- Willing to follow the protocol.

• Able to undergo a brain MRI without anesthesia, as part of routine care (i.e. paid for by their insurance). * Continuously will be defined as no less than 75% of all prescribed doses, with no time of greater than four weeks from last intended dose to have missed a dose (8 weeks for natalizumab, i.e. one missed dose).

Exclusion criteria:

- During original DISCOMS trial participant was randomized to the discontinue group, but then either restarted their DMT during the trial (study-defined 'treatment withdrawal), or wishes to restart their DMT after completing original DISCOMS study. Conversely, also excluded are those who completed the primary trial in the continue group and then discontinued, or wishes to discontinue, after completion of the primary study.
- Any MS relapse or new MRI scan lesion (3 mm or larger) during the primary DISCOMS trial, with relapse determined by the blinded examiner and MRI lesion determined by the blinded MRI reader.
- Significant (as defined by the PI) intolerance of presently-used DMT, if taking a DMT
- The following must **not** have occurred during the original DISCO MS study or since completing the study:
 - Use of any non-FDA-approved DMT
 - More than two courses of acute, systemic (IV or oral). Course is defined as three or more days continuously, and not to exceed 14 days. No use of chronic, systemic steroids, defined as 15 or more days. Any use of steroids to treat MS relapse, possible relapse, or pseudo-relapse is excluded. Inhaled or topical steroids for non-MS are not exclusionary.
 - Use of alemtuzumab, mitoxantrone, cyclophosphamide, methotrexate, cyclosporine, rituximab, or cladribine.
 - \circ $\,$ Use of any experimental agent used as a DMT for MS $\,$
 - Cancers other than basal cell skin cancers

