This will be a non-randomized, rater-blinded pragmatic trial, which is an extension of the randomized discontinuation trial (RDT)⁸², DISCOMS. While RDTs have been done in cancer^{83,84} and rheumatoid arthritis patients,⁶⁶ the original DISCOMS protocol was the first such study in MS. For this protocol, a subset of 100 subjects of the original 260 enrolled will be followed. Study sites will be limited to the top 10 recruiting sites across the United States from the DISCOMS study due to financial and cost-effectiveness issues. Those sites will have participants who have completed 18-24 months of the primary study. In practice, the vast majority, if not all, will have completed 24 months. We will explicitly include any who have completed, including those who already have exceeded 12 additional months after completion of the primary trial. Individuals who have successfully completed (retained original drug assignment and did not meet the primary endpoint of DISCOMS) the primary DISCOMS trial and are willing to retain their original drug assignment after completion and for an additional 12 months will be offered entry into the extension. The only exception to that will be individuals who continued the original drug assignment during and after the primary trial, up to 24 months, but who then had a relapse, new MRI lesion, or other MS-related reason between months 24 and 36 which resulted in their change of medication assignment. These individuals can and should be included, and counted as "failing" during the extension trial completing the Kaplan-Meier event free survival curve critical to the original hypothesis. A total of up to 100 patients will be consented and enter the extension trial, regardless of assignment, on a first come first serve basis to avoid selection biases to the extent possible. The intent is to take the first 100 who fulfill criteria and agree to participate. The plan is for a 50/50 distribution, but there may not be exactly 50 in each group. As of December 15, 2020, 123 had completed participation of the primary 24-month study, and information as to DMT use plans after finishing 2-years participation in DISCOMS was available for 84/123, 42 in each group (see Table 1 below). Notably, in the Discontinue group, 86% remained off DMT while only 60% in the Continue group plan to remain on a DMT (23/42 on the same DMT, two switching to an alternative). Overall 73% remained in the primary assignment grouping. If these ratios stay consistent as more finish DISCOMS, discontinuers will account for roughly 59% of the total enrolled in the extension trial. Also, of the 123 completers, 49 have also gone at least an additional 12 months since completion of DISCOMS, and they will be offered entry into the extension trial, should they otherwise fulfill criteria. There will be no placebo and no sham treatment. (Please see the statistics section the extension ns for power analyses discussions).

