c. Aim #3: Proposed Data Analysis: Descriptive statistics on patient demographics, PDDS, MSIS, performance and NeuroQOL short form scales, and all other PROs will be prepared for treatment group by occurrence of disease event, and qualitatively compared. Pre-Post changes, from baseline and from the entry into the Extension study (with the randomization maintained) will be compared between treatment groups. Change scores will be used for continuous and metric outcomes, and the treatment groups will be compared with two sample T-tests, or Wilicoxon tests if necessary. Binary outcomes, such as dichotomized changes in EDSS and other scales, will be tested with chi-square and proportion tests, or exact methods as necessary. MSIS will be divided into patients with greater or less than a change of 7.5 (considered a significant change). Correlations between continuous scales will be examined, and compared between treatment groups. Events will also be compared to non-events, and combinations of (event outcome) will be tested for differences, using similar methods, in the unlikely situation there are enough events to permit meaningful statistical analysis (>= 10 samples for an analysis group). Multiple groups can be tested with ANOVA methods for continuous outcomes, and with chi-square tests and logistic regression for binary outcomes.

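### Aim 3 compares change scores by arm as if the randomization still held, but entrants are selected after randomization, apparently at different rates by arm, and the planned two-sample tests do not account for it

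*Combined protocol and SAP*

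**What the plan says.** Section III.F, Aim #3 sets out the comparison: "Pre-Post changes, from baseline and from the entry into the Extension study (with the randomization maintained) will be compared between treatment groups". Because baseline is listed separately from entry into the extension, it can only mean the DISCOMS baseline. For continuous outcomes, "the treatment groups will be compared with two sample T-tests, or Wilicoxon tests if necessary".

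Elsewhere the document describes the design differently. Section II calls it a "non-randomized, yet rater-blinded protocol to extend the follow-up of 100 participants from the original DISCOMS cohort", and Section III.C opens with "This will be a non-randomized, rater-blinded pragmatic trial".

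Section III.B makes entry depend on two things that happen after randomization:

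- **Staying event-free.** An exclusion criterion is "Any MS relapse or new MRI scan lesion (3 mm or larger) during the primary DISCOMS trial".
- **Keeping the assignment.** An inclusion criterion reads "Must be willing to continue in their previously-assigned treatment group for the entire, additional 12-Month follow-up period". On the continue side, "also excluded are those who completed the primary trial in the continue group and then discontinued, or wishes to discontinue". Discontinuers who restarted, or wish to restart, are likewise excluded.

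Section III.C allows one exception to the second condition: people who changed medication between months 24 and 36 because of a relapse, a new lesion or another MS-related reason still enter.

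The same section reports that "in the Discontinue group, 86% remained off DMT while only 60% in the Continue group plan to remain on a DMT", and Table 1 gives the counts.

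**The concern.** Randomization makes the arms comparable when everyone randomized is analysed. Here up to 100 of 260 are analysed, and they are chosen partly by what happened to them, and what they decided, after randomization. Change from the DISCOMS baseline is measured over the very period in which that sorting took place.

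The sorting is plausibly related to the outcome. Patients know their assignment, so they decide whether to keep it knowing how they feel on or off drug. That is close to what the quality-of-life, symptom and satisfaction measures record. If the arms are sorted to different degrees, a between-arm difference in change could appear with no treatment effect, or a real one could be hidden.

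Specific Aim 3 asks whether these outcomes are no worse after persistent discontinuation. A reader who takes the parenthesis in the Aim 3 text at face value would give the answer the weight of a randomized comparison.

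**Working it through.** **1. Reproduce the plan's figures (Table 1; Section III.C).**

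- Discontinue arm keeping its assignment: 36/42 = 85.7% (stated 86%).
- Continue arm: (23 + 2)/42 = 25/42 = 59.5% (stated 60%).
- Overall: (36 + 25)/84 = 72.6% (stated 73%).
- Discontinuers among those keeping their assignment: 36/61 = 59.0% (stated 59%).

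All agree.

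**2. Difference between arms.** 85.7% − 59.5% = 26.2 points (95% CI 7.1 to 43.0, Newcombe); odds ratio 4.08; two-sided Fisher p = 0.013. Loss through choice is 17/42 = 40.5% against 6/42 = 14.3%, a ratio of 2.8.

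**3. What that could do to a PRO comparison.** The documents give no link between staying and PRO change, so the following are assumptions: no true difference; staying governed by a normal latent preference with correlation r to PRO change; and 59 against 41 patients, following the plan's projected split.

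If a proportion p stays, the mean change among stayers shifts by r × φ(z)/p SD, where z cuts off the upper proportion p.

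- Continue, p = 25/42: φ(z) = 0.3875, and 0.3875/0.5952 = 0.651.
- Discontinue, p = 36/42: φ(z) = 0.2256, and 0.2256/0.8571 = 0.263.
- Same sign in both arms: gap = (0.651 − 0.263)r = 0.388r SD.
- Opposite signs: gap = (0.651 + 0.263)r = 0.914r SD.
- Standard error of the difference: √(1/59 + 1/41) = 0.203 SD.

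The true rejection rate of a nominal two-sided 5% test is Φ(−1.96 − k) + Φ(−1.96 + k), with k = gap/0.203.

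| r | Gap, same sign (SD) | Error rate | Gap, opposite signs (SD) | Error rate |
|---|---|---|---|---|
| 0.1 | 0.04 | 5.4% | 0.09 | 7% |
| 0.2 | 0.08 | 6.7% | 0.18 | 15% |
| 0.3 | 0.12 | 8.8% | 0.27 | 27% |
| 0.5 | 0.19 | 15.9% | not shown | not shown |

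Selection also narrows the spread within each arm. Allowing for that, the same-sign error rates at r = 0.3 and 0.5 become 9.0% and 17.4%.

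**4. Direction.** If people whose PROs improved tend to stay in both arms, the more heavily sorted continue arm is flattered and discontinuers look worse. If people whose PROs worsened tend to stay in both arms, the sign reverses. If continuers who feel well tend to stop while discontinuers who feel well stay off, discontinuers look better by the larger amount.

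**5. Selection on events.** The documents give no event-free rates by arm, so this part cannot be sized. It could add to the gap or offset it.

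**The case against.** The strongest reply is that the parenthesis means only that patients are grouped by originally assigned arm. The Sample Size text uses similar language for people who keep their assignment, and the document twice calls the extension non-randomized. That reading is fair, and on it the labels are correct. It does not make the groups comparable, and the Aim 3 text invites the stronger reading.

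The plan is also not silent on imbalance. The Sample Size text promises to test for baseline differences using the original trial's data and to adjust for significant ones. This helps in part. But it names no model or variables, significance tests in about 100 people have little power to find imbalance, a two-sample test has no place for covariates, and values at randomization cannot capture tolerability or satisfaction experienced afterwards. Section III.E warns of bias in the PROs, but attributes it to lack of patient blinding. For Aim 2 the plan does recognise that estimates from the origin of the study must be model-based because entrants are selected; Aim 3 has no such step.

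Finally, the last part of Section III.F frames Aims 2 and 3 as describing longer follow-up, and Section III.E concedes low power. This lowers the stakes, but between-arm tests are still specified.

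Four stronger inferences are tempting and not supported:

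- **That 86% and 60% are entry rates.** They come from 84 of 123 completers in December 2020 and are partly stated intentions.
- **That only people who kept their assignment enter.** Section III.C admits those who changed drug for an MS-related reason.
- **That the arms must differ, with discontinuers looking worse.** Both depend on the size and sign of r, on which the documents are silent. At r = 0.1 to 0.2, same sign, the error rate stays near nominal.
- **That modelling all 260 would remove the problem.** T1 values would still come only from selected entrants.

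**Conclusion.** The concern holds in a limited form. Aim 3 as written is a non-randomized comparison of selected persisters, analysed with tests that ignore the selection, and change from the DISCOMS baseline covers the period in which selection occurred. Interim figures suggest selection differs by about 26 points between arms.

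The comparison could be biased in either direction. Under same-sign selection the spurious gap is about 0.39r SD: 0.04 to 0.19 SD for r = 0.1 to 0.5, with a nominal 5% test rejecting about 5% to 16–17% of the time. Opposite-sign selection gives about 0.91r SD. These sizes rest on an assumed latent-normal link, an assumed r and Table 1 holding up in the final cohort. They show what is possible; they do not estimate the bias.

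Aim 3 is secondary and largely descriptive, so the trial's main question is not affected. The wording and analysis should still be changed, because the remedy is cheap and affects what Aim 3 can be said to show.

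**What to change.** 1. In Aim #3, replace the parenthesis with wording such as: by originally assigned group. Label Aim 3 a non-randomized comparison of selected persisters.
2. Make the main comparison an analysis of covariance of the T1 value, adjusted for the DISCOMS exit value, the change during DISCOMS and a prespecified list of baseline covariates, in place of the unadjusted two-sample tests. Table 2 schedules no PROs at T0, so the exit value is the natural starting point.
3. Report extension entry, and reasons for non-entry, by arm.
4. State that change from the DISCOMS baseline in the 100 will not be interpreted as a randomized effect. As a sensitivity analysis, fit a repeated-measures model, or weight for selection, using the existing PRO data of all randomized DISCOMS participants.

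**Cost.** Revised plan text and standard models on data from DISCOMS and the planned T1 visit; no new visits or patients. Item 3 needs reasons for non-entry to be recorded. The sensitivity analysis assumes data are missing at random given what DISCOMS recorded, which fails if an unmeasured preference drives staying, so it is only a partial remedy. The conclusion Aim 3 can support becomes more modest.

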 - iii. Patient Determined Disease Steps (PDDS disability): The Patient-Determined Disease Steps (PDDS) is a PRO version of the clinician-reported Extended Disability Status Scale (EDSS) which hones the stages of cane use and thus is more responsive to mid-range disability changes.⁷⁹ This tool asks the patient to characterize level of disability into one of nine steps (0=normal, 1=mild disability, 2=moderate disability, 3=gait disability, 4=early cane, 5=late cane, 6=bilateral support, 7=wheelchair scooter, 8=bedridden). The PDDS will be used to characterize (and to control for) disability in both study groups at all study time points.
 - iv. **The Symbol Digit Modalities Test (SDMT cognition):** The SDMT measures patient attention, concentration, and speed of information processing and has been validated for discriminating patients from controls even when it was administered each month over six months.⁸⁰ It is relatively simple to administer and only takes a few minutes to complete.
 - v. **Multiple Sclerosis Impact Scale (MSIS-29 MS symptoms**): Since Neuro-QoL short form doesn't have the ability to provide an overall quality of life calculation, the study team added MSIS-29, which is an acceptable, reliable, and valid method for recording quality of life in MS patients.⁸¹
 - vi. **Treatment Satisfaction Questions:** This was developed for qualitative and exploratory purposes. These questions will provide insight into patient satisfaction in regards to the disease modifying therapy (DMT) they are using at baseline, versus their ongoing satisfaction with their study care plan (on a DMT v. not on a DMT). The following question will be asked:

How satisfied are you with your current DMT (or lack of DMT)? Please circle one.

Very dissatisfied Dissatisfied Neutral Satisfied Very satisfied

vii. **Treatment Decision Questions**: These questions were also developed for exploratory purposes to gain insight on the MS DMT treatment decisions at the conclusion of the study and to better understand recruitment and retention, for patients who were randomized to either staying on or going off their DMT. The following questions will be asked:

What do you plan to do for your MS medication after completing the study? Please circle one.

If you are in the continue group:		
Stop my DMT	Continue my current DMT	Switch to a new DMT
If you are in the discontinue group:	-	
Stay off of my DMT	Re-start a prior DMT	Re-start a new DMT

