Sample Size: The sample size was driven by budget considerations and the expected number who could complete the extension within a reasonable time period. We chose to focus on those who have been maintained in their assigned treatment arms from the original randomization to allow extension of time to event analyses. We considered including those who would go back on therapy or who subsequently stopped therapy, but felt that not only would the numbers likely be smaller than desired, they would diminish the available slots for the most informative participants (those maintaining their randomized assignment). Thus, while we expect roughly equal numbers from both treatment arms (the alternative hypothesis originally posed, that the two treatments are equal), we will have approximately 50 participants per arm. If we assume that there are 50 participants in each arm and 20% of the discontinue arm fails compared to 6% (10 and 3 of each group respectively), a fisher's exact test would yield a one sided p-value of 0.036, sufficient to say the discontinue group has done worse. We also plan to test for baseline differences between the two groups, using data from the original RCT, and will adjust for any significant baseline differences.

It may be that there are differences between those with relapsing forms vs progressive forms of MS after discontinuation of their DMT. While we will not be powered to assess differences separately by relapsing or progressive forms, we have a pre-planned descriptive analyses for this important question, as well as other subgroup analyses. These will include analysis based on sex, age, disease duration, time since last relapse, specific DMT, and others since study outcomes will not be powered for stratification by MS type or heterogeneity of treatment effects, they will be simply examined as estimates of longer term treatment follow-up.

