Similarly, we are making the assumption that risk of discontinuation to achieve the primary endpoints in Aim #1 will be similar for different DMTs, and for different subtypes of MS, i.e. relapsing vs progressive forms. To assess each medication individually would not be possible given the study constraints, and there is no a priori data to consider the risks different in this patient group, i.e. older, stable patients. While it may not be true, ultimately, that risks of new inflammatory disease activity after discontinuation of DMT are the same in relapsing and progressive MS patients, or that risk of relapse is the same in each group, there are no data on this point in this population, i.e. older, stable patients. For the purposes of the analysis, we are assuming there are no expected differences. For secondary outcomes AIMS 2-3, a two sample estimates of the differences in change scores between treatment groups will be calculated for describing the longer term follow-up.

We will continue to assess safety as was done during the primary DISCOMS trial to ensure there are no late effects or concerns developing. We will continue to monitor AEs and SAEs including those which occur from the discontinue group if they return to treatment.

G.Summarize Knowledge to be Gained:

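### Continuous Aim 3 outcomes and mean EDSS change are compared as raw change scores, with baseline adjustment only if a baseline difference is significant; the outcome's own pre-randomization value should always be in the model

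*Combined protocol and SAP*

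**What the plan says.** Section III.F.c (Aim #3: Proposed Data Analysis) sets two reference points for change: "Pre-Post changes, from baseline and from the entry into the Extension study (with the randomization maintained) will be compared between treatment groups". I read the first as the original DISCOMS baseline, because it is contrasted with extension entry. The same section then gives the method: "Change scores will be used for continuous and metric outcomes, and the treatment groups will be compared with two sample T-tests". Wilcoxon tests are the fallback, and no covariate is named.

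The closing part of section III.F repeats this for Aims 2 and 3, which brings in mean EDSS change: "a two sample estimates of the differences in change scores between treatment groups will be calculated for describing the longer term follow-up".

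Two other passages bear on adjustment:

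- The Sample Size paragraph of III.F: "We also plan to test for baseline differences between the two groups, using data from the original RCT, and will adjust for any significant baseline" (cut here one word before its end). This rule names no variables, test level or model.
- Section III.A, under the PDDS: "The PDDS will be used to characterize (and to control for) disability in both study groups at all study time points". No analysis model is attached to this.

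On size, the Sample Size paragraph says that the number was set by budget and feasibility, and that "we will have approximately 50 participants per arm". Section III.C calls the extension non-randomized and projects about 59% discontinuers.

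**The concern.** To form a change from baseline, the analyst must already hold the baseline value of each scale. A change score subtracts that value with its coefficient fixed at 1. Regression on baseline estimates the coefficient instead. With equal SDs at the two times, the within-arm slope is the correlation r, which is below 1. Fixing it at 1 adds noise, and any chance imbalance at baseline carries over into the arm difference through regression to the mean.

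The plan accepts baseline adjustment in principle but makes it depend on a significance test. That has two drawbacks. When the groups look balanced, nothing is adjusted and no precision is recovered. When they do not, the model is chosen after seeing the data, possibly differently for each scale.

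With at most 100 participants and no means of adding more, the analysis is the one place where precision can still be gained for these outcomes.

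**Working it through.** **The plan's own figures.** Table 1 has 36 of 42 discontinuers and 23 + 2 = 25 of 42 continuers keeping their assignment. 36/(36+25) = 0.590, which reproduces the projected 59%. For 100 participants this gives 59 v 41. The documents state no SD, margin, power or baseline-to-follow-up correlation for Aim 3, so there is no Aim 3 figure to reproduce.

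**Assumptions.** SD equal at both times and set to 1; correlation r between the baseline and T1 values; baseline differences between arms due to chance. The last is relaxed in the final step.

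**Formulas.**

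- Variance factor: change score 2(1-r); regression on baseline (ANCOVA) 1-r².
- Ratio, change score to ANCOVA: 2(1-r)/[(1-r)(1+r)] = 2/(1+r), whatever the allocation. The gain in equivalent participants is 2/(1+r)-1.
- Standard error multiplier at 59 v 41: sqrt(1/59 + 1/41) = 0.203.
- 95% half-width: 1.96 × 0.203 × sqrt(variance factor).

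| r (assumed) | Change-score factor | ANCOVA factor | Gain | Half-width, change score (SD) | Half-width, ANCOVA (SD) |
|---|---|---|---|---|---|
| 0.3 | 1.40 | 0.91 | 54% | 0.47 | 0.38 |
| 0.5 | 1.00 | 0.75 | 33% | 0.40 | 0.35 |
| 0.6 | 0.80 | 0.64 | 25% | 0.36 | 0.32 |
| 0.8 | 0.40 | 0.36 | 11% | 0.25 | 0.24 |
| 0.9 | 0.20 | 0.19 | 5% | 0.18 | 0.17 |

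A simulation at 59 v 41 (20,000 runs per setting, no true baseline difference) gave variance ratios of 1.33 at r = 0.5 and 1.10 at r = 0.8, in line with the formula.

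**When would the plan's rule act?** The plan gives no test level. At two-sided 5%, the observed baseline difference must reach about 1.96 × 0.203 = 0.40 SD. With no true difference, that happens for about 5% of scales. An imbalance of 0.2 SD, about one standard error, would not trigger it. If the imbalance is chance, the change score carries (1-r) × imbalance into the arm difference:

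- at 0.2 SD: 0.04 SD (r = 0.8) to 0.10 SD (r = 0.5);
- just under the 0.40 SD trigger: 0.08 SD (r = 0.8) to 0.20 SD (r = 0.5).

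**If the imbalance is not chance.** Suppose the groups differ stably by 0.3 SD at baseline and change equally. The change score then gives 0, while ANCOVA gives (1-r) × 0.3 = 0.06 SD at r = 0.8 and 0.15 SD at r = 0.5. The simulation gave 0.060 and 0.152, with variance ratios of 1.07 and 1.30.

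**The case against.** The strongest objection is about design. The variance formula and the regression-to-the-mean argument belong to randomized groups, and section III.C says that the extension is not randomized. Entry depends on having kept the assignment, and Table 1 shows 36/42 against 25/42 doing so. If those who stayed on or off treatment differ stably at baseline, ANCOVA can be the biased method, as the last step of the working shows. This stands. A reader might infer that the change score is biased and ANCOVA is not, but the documents do not say whether any imbalance would be chance or selection. Equally, they do not show that a stable difference exists. If retention depended on the baseline score itself, conditioning on that score would address it and subtraction in general would not. This is a reason to fix one primary model in advance and show the other.

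Three other readings go too far:

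- *That the plan never adjusts.* It does, conditionally, under the Sample Size paragraph, and it mentions controlling for disability by PDDS. The weakness is the trigger and the missing model.
- *That the plan forgoes a known 11% to 33% of its sample.* That range is r = 0.8 to 0.5, and no r is given. At r = 0.8 the half-width barely moves. The number enrolled is capped by budget, so the cost is wider intervals and not a wrong sample size.
- *That the same argument covers change from extension entry.* That starting value is measured after 18 to 24 months on or off treatment, so adjusting for it is not a pre-randomization adjustment.

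It is also fair to say that Aim 3 has no margin, that section III.F describes these estimates as descriptive, and that section III.E concedes both low power for non-inferiority and possible patient bias in the PROs. Comparing change scores is a valid, common choice in that setting. But section III.F.c still specifies between-group tests, and a descriptive difference also benefits from a narrower interval and a model fixed in advance.

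**Conclusion.** The point holds for the comparison of change from the original DISCOMS baseline, for continuous Aim 3 outcomes and for mean EDSS change measured from that baseline. The significance-triggered rule leaves the outcome's own baseline unused in most cases and makes the model depend on the data.

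The gain from always including it ranges from 54% in equivalent participants at r = 0.3 to 5% at r = 0.9, so it may be useful or negligible. It rests on an assumed r, equal SDs and chance imbalance. The 0.40 SD trigger rests on an assumed two-sided 5% test and the projected 59 v 41 split. Adjustment does not remove selection into the extension, and neither does the change score. This is a modest improvement at almost no cost and does not mean that the planned analysis is invalid.

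**What to change.** In sections III.F.c and III.F (secondary outcomes):

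1. For change from the original DISCOMS baseline, make the main analysis of each continuous Aim 3 outcome, and of mean EDSS change, a linear regression of the T1 value on arm and the pre-randomization value of the same scale. Always include that covariate. Report the arm difference with its 95% interval.
2. For these outcomes, remove the rule that tests baseline differences and adjusts for the significant ones.
3. Show the unadjusted change-score difference, with the planned t-test or Wilcoxon result, as a sensitivity analysis. State that the groups are self-selected, that the two methods can target different quantities, and that any disagreement will be discussed.
4. Keep change from extension entry as a separate comparison, and state that its starting value is measured after randomization. If that value is used as a covariate, say that the result is conditional on status at entry.
5. If a precision gain is quoted, give it as 2/(1+r)-1 with r labelled as an assumption.

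The cost is SAP wording. No new data are needed, since the baseline values are already required to compute the changes. The one downside is the possible disagreement in item 3.
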